Physical Function of Older Citizens During Municipality- based Rehabilitation - Statistical Analysis Plan

ClinicalTrials.gov Identifier: NCT04862481

Version: 1, December 14, 2021

Roles and responsibility:

[name]. student, **principal investigator**
Center for Nutrition and Rehabilitation, Department of Physiotherapy,
University College Absalon, [name] &
Department of Sports Science and Clinical Biomechanics, University of
Southern Denmark.
[contact] / [contact]

[name], assistant professor, **supervisor**
Department of Sports Science and Clinical Biomechanics, University of
Southern Denmark.
[contact]

[name], assistant professor, **supervisor**
Department of Sports Science and Clinical Biomechanics, University of
Southern Denmark.
[contact]

[name], associate professor, **supervisor**
Center for Nutrition and Rehabilitation, Department of Physiotherapy,
University College Absalon.
[contact]

[name], professor, **supervisor**
School of Sport, Exercise and Rehabilitation Sciences, University of
Birmingham, UK.
[contact]

[name], professor emeritus, **supervisor**
Department of Sports Science and Clinical Biomechanics, University of
Southern Denmark.
[contact]

[name], professor, **principal supervisor**
Department of Sports Science and Clinical Biomechanics, University of
Southern Denmark.
[contact]

*This statistical analysis plan is based on the SAP guidelines presented by Gamble et al.(1)

Introduction

When choosing outcomes to assess the effectiveness of a physical rehabilitation program, it is essential to consider the constructs being measured and their value to the patient and the psychometric properties. Choosing an outcome that reflects all aspects of International Classification levels of Functioning, Disability and Health (ICF) is challenging, especially in heterogeneous groups. However, it is important to know the psychometric properties as this gives important knowledge on how to interpret results and, consequently, how this can inform the patient's care.

The Short Musculoskeletal Function Assessment (SMFA) questionnaire can reflect differences in patients' functional status with a broad range of disorders, like for older citizens undergoing municipality-based physical rehabilitation. This is also why we have chosen the SMFA as the primary outcome in our randomized controlled trial (2).

Nevertheless, since there is no golden standard to measure physical rehabilitation outcomes, construct validity needs to be established to investigate how scores of SMFA can be related to measures on all levels of ICF.

Objectives

Therefore, this cross sectional study on older citizens referred to municipality-based rehabilitation has three main objectives:

1. To investigate how scores of the SMFA questionnaire are related to measures on different ICF levels
2. To describe the characteristics of older citizens starting municipality-based rehabilitation on all ICF levels
3. To investigate predictor variables of upper- and lower extremity strength

Study methods

Trial design

This study was designed as a descriptive observational cross-sectional study.

Sample size

The sample size references the number of participants to include in the study to answer the first objective regarding construct validity. To detect a correlation coefficient of minimum $r = \pm 0.3$ with a significance level of 0.05 and power of 0.8 between the primary outcome SMFA and the generic health-related quality of life questionnaire SF36, a minimum of 85 participants were needed based on the Fisher's z test. Some studies have shown a response rate for the SMFA to be approximately 65% in cross sectional studies (3). We, therefore, added another 35% extra participants to the calculated sample size, resulting in a target of 115 participants to be initially included in the study.

Statistical principles

P-values and statistical significance

A two-tailed probability value of $p \leq .05$ will be considered statistically significant, and estimates will also be presented with 95% confidence intervals.

Descriptive statistics

Descriptive data and fitted regression residuals from linear regression models will be inspected visually for Gaussian distribution by QQ-plots and frequency histograms and tested statistically with the Shapiro-Wilk test. Parametric and/or non-parametric statistical analysis will be used appropriately. Where appropriate, variables will be summarized by means and standard deviations, otherwise as medians with interquartile ranges. Categorical data will be summarized using counts and percentages.

Correlations

Pearson correlation coefficient and Spearman's Rank-Order correlation will be used based on the fulfilment of assumptions.

Correlation coefficients between $r = .1-.25$ represent a weak correlation, $r = .25-.50$ a fair correlation, $r = .5-.75$ a moderate correlation and above $r = .75$ a strong correlation (4).

Regression models

Mixed linear and quantile regression models will be used based on the fulfilment of assumptions.

Subgroup analysis/exploratory analysis

Since the targeted population might vary considerably for their primary reason of referral to rehabilitation, participants will be divided into clinically meaningful subgroups: Lower extremity disorders, upper extremity disorders, spinal disorders.

Trial population

Screening data

Screening data has been logged. Age, gender, reason for referral to physical rehabilitation and reason for exclusion is available to describe representativeness of the included population.

Target group

115 men and women from Slagelse municipality's community-based health centre were recruited in the period January 2021- Sept 2021 (Fig. 1 - Flow chart).

Eligibility

Inclusion Criteria

All citizens that were referred to the health/rehabilitation center aged ≥ 65 years from Slagelse municipality were invited to a screening interview with a physiotherapist after which the participant was asked to join the study if not subject to one of the following exclusion criteria's:

Exclusion Criteria:

- Inability to speak or read Danish,
- Active cancer,
- Upper or lower limb amputations,
- Hypertension $>180/90$,
- Referred to rehabilitation primarily due to gynecological or neurological conditions (apoplexies) or surgeries where movement restrictions prohibit participating in most of the tests,
- Discouragement from a general practitioner

Recruitment

Fig. 1 - Flow Chart "EXAMPLE"

[figure not shown]

Fig.1: Flow chart of recruitment process.
 * Other indicate complex health issues that excluded the patients from participating in most of the selected tests (< 50% of the tests).

Statistical Analysis Plan

Participant characteristics

Table 1 - Characteristics of the participants

Gender, male/female, n(%)	
Age, years	
	65-79
	≥ 80
Weight, kg.	
BMI, kg/m ²	
Clinical groups, n(%)	
	Lower extremity
	Upper extremity
	Spinal
Primary reason of referral, n(%)	
Comorbidities, n(%)	
	0
	1-2
	2-3
	>4
Medication, n(%)	
Level of education completed, n(%)	
	Primary school
	Secondary school
	Higher education
Living alone, Yes/No, n(%)	
Annual income, n(%)	
Physical activity level, n(%)	
	Sedentary
Standing or walking, without physical exertion	
Standing or walking with several lifting or carrying activities	
Strenuous physical activities	

Gaussian distributed data is presented as means ± SD, otherwise as medians with interquartile range.

Lower extremity clinical group definition:

Upper extremity clinical group definition:

Spinal clinical group definition:

Statistical Analysis Plan

Analysis

Outcome definitions

Primary outcome

Short Musculoskeletal Function Assessment (SMFA)

Scores for the SMFA is divided in a dysfunction index SMFA-D and a bother index SMFA-B.

Assessing

Functional status.

Instrument / equipment

Self-reported
Questionnaire

Secondary outcome

Short Form 36 (SF-36)

Health-related quality of life.

Self-reported
Questionnaire

Other outcome measures

The New Mobility Score (NMS): composed score of physical mobility. Each question is scored between 0-3 points, depending on the degree of walking aid is used. help. The total possible score is between 0 and 9 points. Higher scores indicate better mobility.

Walking function inside, outside, and during shopping. Including whether a walking aid is used.

Self-reported
Questionnaire

PRISMA-7: composed score of frailty - each question scores either 0 or 1 points. The total possible score is between 0 and 7 points. Lower scores indicate less frailty.

Frailty/risk of frailty.

Self-reported
Questionnaire

Statistical Analysis Plan

Tilburg Frailty Indicator (TFI): bio-psycho-social approach, which measures frailty. It is composed of 15 multidimensional questions, regarding the physical, psychological, and social aspects of human functioning. Scoring range is between 0-15 points.
	
Frailty/risk of frailty.
	
Self-reported Questionnaire

A survey with self-formulated questions regarding name, sex, personal ID (CPR number), educational level, the region of pain the last three months (marked on a body chart), pain intensity and pain duration at the most painful body region the last three months, and physical activity level.
	
Musculoskeletal pain (region of pain, intensity of pain, duration of pain), physical activity level and demographic information.
	
Self-reported Questionnaire

Weight
	
Weight in kilograms.
	
Tanita 9MC-780U Multi Frequency Segmental Body Composition Analyzer (Tanita, Tokyo, Japan)

Height
	
Height in meters.
	
Etopoo stadiometer (China)


Blood pressure
	
Systolic and diastolic blood pressure in mmHg.
	
Tanita 9MC-780U Multi Frequency Segmental Body Composition Analyzer (Tanita, Tokyo, Japan)

Resting heart rate
	
Resting heart rate in beats per minute (BPM).
	
Omron HBP 1100 (Omron, Kyoto, Japan)

Statistical Analysis Plan

Lean body mass	Total and segmental lean body mass in kilograms.	Tanita 9MC-780U Multi Frequency Segmental Body Composition Analyzer (Tanita, Tokyo, Japan)
Fat percentage	Total and segmental body fat in percent of the total body mass.	Tanita 9MC-780U Multi Frequency Segmental Body Composition Analyzer (Tanita, Tokyo, Japan)
Total body water	Total body water in percent of the total body mass.	Tanita 9MC-780U Multi Frequency Segmental Body Composition Analyzer (Tanita, Tokyo, Japan)
Visceral fat score on a scale ranging between 1-59.	Visceral fat level	Tanita 9MC-780U Multi Frequency Segmental Body Composition Analyzer (Tanita, Tokyo, Japan)
Basic metabolic rate (BMR)	BMR in kilojoules.	Tanita 9MC-780U Multi Frequency Segmental Body Composition Analyzer (Tanita, Tokyo, Japan)

Statistical Analysis Plan

Waist-To-Hip ratio	Distribution of fat and overall health. The waist-To-Hip ratio is calculated by measuring the circumference of the waist (in centimeters) and dividing it with the circumference of the hip (in centimeters) to report the Waist-to-hip ratio.	Non elastic plastic measuring tape (Producent not specified)
Maximal torque in knee extension	Maximal isometric strength in knee extension (MVIC). The MVIC will be calculated by multiplying produced force and the length of the moment arm.	Strain gauge (SDU, Odense, Denmark)
Handgrip strength	Maximal isometric strength of handgrip.	SAEHAN hydraulic dynamometer (Saehan, Masan, South Korea)
Shoulder strength	Shoulder abduction strength in kilograms using a handheld dynamometer.	MicroFET2 (Utah, USA)
Elbow strength	Elbow flexion and extension strength in kilograms using a handheld dynamometer.	MicroFET2 (Utah, USA)

Statistical Analysis Plan

Leg press strength	Five repetitions maximum strength test in leg press in kilograms.	Technogym training equipment (Technogym, Cesena, Italy)
Knee extension strength	Five repetitions maximum strength test in knee extension in kilograms.	Technogym training equipment (Technogym, Cesena, Italy)
Calf extension strength	Five repetitions maximum strength tests in calf extension in kilograms.	Technogym training equipment (Technogym, Cesena, Italy)
2-minute walk test	Gait speed and distance. Gait speed will be calculated by dividing the covered distance with the time in seconds. Heart rate (in BPM) and perceived exertion (BORG 6-20) are collected pre- and post-testing.	Course 15.2 meters Stopwatch Apple Watch series 5 The Borg Rating of Perceived Exertion 6-20 scale
Timed Up and Go test (TUG)	Time noted in seconds on how long it takes to get up from a chair, walk three meters, turn around and go backheight) to the chair and sit down again.	Course 3 meters Chair (46 centimeters in height) with armrests Stopwatch
Tandem test	Static balance Balance is tested in three positions for ten seconds each (feet together,	Stopwatch

Statistical Analysis Plan

semi tandem, and full tandem). Time is noted in seconds for how long the participant can stand in each position.

Balance test and reaction test for upper and lower extremities

Balance test:

Fysiometer software

Velocity of the center of pressure in (Brønderslev, Denmark)

mm/sec.

Nintendo Wii Balance Board

Ellipse area for the center of

(Kyoto, Japan)

pressure in mm².

Reaction test:

Average reaction time in milliseconds

(ms) of seven reaction tests.

Food interviews

Intake of total energy intake and

Vitakost software

macronutrients based on 24-hour

(Kolding, Denmark)

dietary recall interviews.

History of falls

Interview regarding history of fall

Interview

within the last year

Statistical Analysis Plan

Analysis methods

- For objective 1:

- Under the assumption of normally distributed data, Pearson correlation coefficients will be calculated and presented with p values and 95%CI. Otherwise as Spearman's rank order correlation coefficients.
- Correlations will be conducted between SMFA-D/SMFA-B and measures on different ICF levels:
 - SMFA-D/SMFA-B and clinical measures (*upper extremity strength, lower extremity strength, body composition, gait test, TUG test, balance tests, reaction tests*).
 - SMFA-D/SMFA-B and other questionnaires (*SF36 health survey, Tilburg Frailty Indicator, PRISMA-7, and NMS*).
- Cronbach's alpha will be calculated to investigate the internal consistency of the specific categories of the SMFA (*daily activities, emotional status, arm and hand function category, mobility*). Cronbach's alpha above .70 are usually acceptable(5).
- Under the assumption of acceptable Cronbach's alpha values, same correlations will be conducted between specific categories of the SMFA and the different levels of ICF.
- Under assumption of normally distributed data, two tailed unpaired t-tests will be conducted to investigate differences in SMFA-D/SMFA-B scores and presented baseline characteristics. Otherwise, a Mann-Whitney U test will be conducted.

- For objective 2:

- Under the assumption of normally distributed data, summary statistics will be presented as means with standard deviations, otherwise as medians with interquartile ranges. Categorical data will be presented with counts and percentages.
- Summary statistics will be presented for the total sample and for each clinical group.

- For objective 3:

- Under the assumption of normally distributed data, linear regression models will be conducted to investigate whether handgrip strength can be a predictor/proxy of upper extremity strength. Otherwise, quantile regression models will be conducted.

Statistical Analysis Plan

- Upper extremity strength measures (elbow extension, elbow flexion, shoulder abduction) will be set as the dependent variable and hand grip strength of the same arm as the predictor variable. Other explanatory variables to be fitted in the model will be: *age, gender, and height* since these variables affect hand grip strength(6). Other variables added in the model are the fat free mass and knee extension strength(7).

Hypothesis

- SMFA-D and SMFA-B are strongly correlated with each other(8).
- SMFA-D and SMFA-B scores are fair to moderately negatively correlated with the following clinical measures: handgrip strength, MVIC of knee extension, tandem balance test, 2-minute walk test, Leg press strength, knee extension strength and calf extension strength. Further, we hypothesize that the SMFA-D will show higher negative correlations with mentioned clinical measures than the SMFA-B (8).
- SMFA-D and SMFA-B are moderate to highly correlated with other health-related questionnaires and frailty indicators: SF36 (negative association), Tilburg Frailty Indicator (positive association), PRISMA7 (positive association) and NMS (positive association) (9, 10).
- We hypothesize that specific functional areas on the SMFA will not be as strongly related to the sum score of SMFA as they will be to a specific category (8).
- We anticipate low physical and functional scores of the total sample (11).
- Handgrip strength is a good proxy of upper extremity strength (elbow extension, elbow flexion and shoulder abduction)(12).

Missing data

- We do not expect missing values to be greater than 5 percent for the SMFA, besides the sexual activity question (8). Scoring instructions for the SMFA will be followed, and missing responses will be handled as suggested by the original authors (13).
- We anticipated that some participants would not complete all clinical tests due to discomfort, pain, or fear of injury. In these circumstances, those participants will be excluded from the specific analysis.

Statistical software

Data will be analyzed using StataBE ver. 17 (StataCorp. 2021. *Stata Statistical Software: Release 17*. College Station, TX: StataCorp LLC.).

Protocol deviations

Minor adjustments were made after trial registration on Clinicaltrials.gov.

- Due to the COVID19 lockdown, some facilities in the municipality were closed. We, therefore, needed to adjust the testing setup for some tests.
- The course for the 2 min walk test (2MWT) was changed from 30 meters to 15.2 meters.
- The waiting time between some tests were a bit longer (~10 min.) than planned due to other patients' rehabilitation practice in the health centre. Each testing session took roughly 90-100 minutes to conduct.
- Due to a changed recruitment strategy (more people were screening for eligibility due to task shifting), several citizens were missed and therefore not asked to participate in the study. Further participants were hesitant to participate in the study due to COVID-19. Therefore, the result was a more extended recruitment period than initially described.

References

3. Hunsaker FG, A. D, Cioffi M. The American Academy of Orthopaedic Surgeons Outcomes Instruments Normative Values From the General population. *The Journal of Bone and Joint Surgery*. 2002.
5. Cortina JM. What Is Coefficient Alpha? AN Examination of Theory and Applications. *Journal of Applied Psychology*. 1993;78:98-104.

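### The target of 115 does not allow for the 65% SMFA response rate it is based on: 131 would be needed, and 115 leaves about 75 evaluable against a minimum of 85

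*SAP*

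**What the plan says.** The Sample size section (under Study methods) sizes the study for objective 1, construct validity, on the correlation between the SMFA and the SF-36. The target correlation is 0.3 in either direction, "with a significance level of 0.05 and power of 0.8". From this the SAP concludes that "a minimum of 85 participants were needed based on the Fisher's z test".

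It then cites an SMFA response rate of about 65% in cross-sectional studies (its reference 3) and draws the recruitment target from it: "We, therefore, added another 35% extra participants to the calculated sample size, resulting in a target of 115 participants to be initially included".

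Four other places bear on the point:

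- **P-values and statistical significance** sets two-tailed testing at 0.05.
- **Target group** reports that 115 men and women from the municipality's "health centre were recruited in the period January 2021- Sept 2021".
- **Hypothesis** expects a moderate to high correlation, negative in sign, between the SMFA indices and the SF-36. **Correlations** starts the moderate band at 0.5.
- **Missing data** expects no more than 5% missing values on the SMFA, apart from the question on sexual activity.

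**The concern.** The 65% rate is the stated reason for the 35% addition, 115 is the number before loss, and 85 is the number needed after it. Read together, these statements say that including 115 people protects 85 evaluable participants at 65% response. It does not. The 35% loss falls on everyone included, whereas the SAP took 35% of the smaller figure of 85. The addition is therefore too small.

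If the cited response rate occurred, objective 1 would be analysed on fewer participants than the SAP's own minimum, with less than the stated power at the correlation it chose to detect. A reader checking the sample size justification would find that it does not provide the protection it describes.

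**Working it through.** **Inputs, all from the SAP.** r = 0.3, alpha 0.05, power 0.8, minimum 85, response rate 65% and target 115 come from Sample size. Two-sided testing comes from P-values and statistical significance.

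**1. Reproduce the 85.** Fisher's z, with atanh(0.3) = 0.3095:

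n = ((1.960 + 0.842) / atanh(0.3))² + 3 = 84.93, rounded up to **85**. This agrees with the SAP. A one-sided test would give 68, so the calculation is two-sided.

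**2. Reproduce the 115.** 85 × 1.35 = 114.75, rounded up to **115**. This is the SAP's rule.

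**3. Apply the response rate to those included.** If N people are included and 65% respond, 0.65 × N must be at least 85:

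- N = 85 / 0.65 = 130.8, rounded up to **131**
- Check: 131 × 0.65 = 85.15, and 130 × 0.65 = 84.5, which is too few
- Shortfall in the target: 131 − 115 = 16

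**4. What 115 delivers.**

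- Evaluable at 65% response: 115 × 0.65 = 74.75, **about 75**, which is ten below 85
- Break-even response: 85 / 115 = 73.9%, so 115 covers 26.1% non-response and not 35%
- If each of 115 people responds independently with probability 0.65, the chance of reaching 85 responders is about 2.6%

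**5. Consequence for the test.** Power = Φ(atanh(r) × √(n − 3) − 1.960); detectable r at 80% power = tanh(2.802 / √(n − 3)); critical |r| = tanh(1.960 / √(n − 3)).

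| | n = 75 | n = 85 |
|---|---|---|
| Power at true r = 0.3 | 0.747 | 0.800 |
| Detectable r, 80% power | 0.319 | 0.300 |
| Critical \|r\|, two-sided 5% | 0.227 | 0.213 |

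With all 115 evaluable, power at r = 0.3 would be 0.906.

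**6. At the correlation the SAP expects.** Taking r = 0.5, the lower edge of its moderate band, with atanh(0.5) = 0.5493: at n = 75, Φ(0.5493 × √72 − 1.960) = Φ(2.701) = 0.9965.

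**The case against.** Three arguments can be made for leaving the text alone.

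**The sum is literally correct.** The SAP says it added 35% to 85, and 85 plus 35% is 115. That is true, and the fault is best described as the wrong inflation rule, not a slip in multiplication. But the addition is justified by the 65% rate, and it does not serve that purpose. The word approximately before 65% does not cover the gap either, because the break-even of 73.9% is almost nine percentage points higher.

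**Losses may be much smaller.** Missing data expects at most 5% missing SMFA values. If that were the only loss, 115 × 0.95 = 109 would be evaluable, and power at r = 0.3 would be Φ(0.3095 × √106 − 1.960) = Φ(1.227), about 0.89. This stands as a reason to treat 75 as one scenario and not a forecast. It does not mend the sizing, because that section concerns missing values and the target was built on a response rate.

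**The 65% may describe response to a survey invitation.** The SAP does not say which it is. Refusals would then fall before inclusion, and neither 115 nor 131 would follow from the rate. This also stands, so 131 is conditional on the SAP's own use of the figure. The inflation sentence would still need correcting, since it applies the rate to people already included.

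The consequence is also limited: recruitment was over before the SAP was dated 14 December 2021, and no analysis depends on the target.

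**Conclusion.** The concern holds, at minor severity. On the SAP's own assumption that 65% of those included respond, the target should have been 131, and 115 gives about 75 evaluable participants where at least 85 were required. The cost is about five percentage points of power at r = 0.3 (75% against 80%), or a detectable correlation of 0.32 in place of 0.30.

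This rests on reading the 65% as response after inclusion, which is how the SAP uses it. If response was 74% or better, the minimum of 85 was met. If the true SMFA–SF-36 correlation is 0.5 or more, as hypothesised, power is above 99% either way. What needs correcting is a stated planning figure; the conduct of the study is not affected.

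**What to change.** Replace the inflation sentence in Sample size with wording such as:

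> If 65% of those included respond, retaining 85 participants would have required 85/0.65 = 131. The target used was 115, which retains 85 if at least 74% respond; at 65% response it would give about 75 evaluable participants and about 75% power for a true r of 0.3.

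It would help to add whether the cited 65% refers to invited or to enrolled people.

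In the results, give the number of participants with both SMFA and SF-36 scores beside the planned correlation and its 95% confidence interval. Once data are in, that count and interval tell the reader more than any planning figure.

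The cost is a short wording change and one reported count. No further enrolment, data collection or change of analysis is needed.

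### The SAP names only two-group tests for SMFA by baseline characteristics, although four of the seven Table 1 characteristics with printed levels have three or four; separately, the comorbidity bands overlap at 2 and omit 4

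*SAP*

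**What the plan says.** The SAP's Analysis methods section, under objective 1, states that, if data are normally distributed, "two tailed unpaired t-tests will be conducted to investigate differences in SMFA-D/SMFA-B scores and presented baseline characteristics". The next sentence gives the alternative: "Otherwise, a Mann-Whitney U test will be conducted". No other procedure is assigned to this comparison.

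Table 1, under Participant characteristics, lists the baseline characteristics. Some rows print their levels, for example the rows under "Level of education completed, n" (three school levels) and under "Comorbidities, n" (four bands: 0, 1-2, 2-3, >4). The section on subgroup analysis says that "participants will be divided into clinically meaningful subgroups: Lower extremity disorders, upper extremity disorders, spinal disorders".

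Under Statistical principles, Descriptive statistics, there is a general sentence: "Parametric and/or non-parametric statistical analysis will be used appropriately". For objective 2 the SAP plans description only: "Summary statistics will be presented for the total sample and for each clinical group", and "Categorical data will be presented with counts and percentages".

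**The concern.** An unpaired t-test or a Mann-Whitney U test needs exactly two groups. Where a characteristic has three or four levels, the sentence cannot be carried out as written. Analysts following the same text could test only the two-level characteristics, use one overall test for each of the others, collapse levels after seeing the data, or test pairs. They would report different results. The SAP attaches a two-sided 0.05 threshold to its tests, and the purpose of writing the rule down is to settle that choice beforehand.

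The comorbidity bands are a second, unrelated defect in the same table. Describing the participants is objective 2. Bands that are neither exclusive nor exhaustive cannot give a valid distribution of n and percent.

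**Working it through.** The SAP gives no figure of its own on this point, so there is nothing to reproduce. The check is a count and a comparison of the text.

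**1. Levels printed in Table 1**

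| Characteristic | Printed levels | Fits a two-group test? |
|---|---|---|
| Gender | 2 | yes |
| Age band (65-79, ≥ 80) | 2 | yes |
| Living alone | 2 | yes |
| Clinical group | 3 | no |
| Education | 3 | no |
| Comorbidities | 4 | no |
| Physical activity | 4 | no |

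That is 3 + 4 = 7 characteristics with printed levels, and 4 of the 7 have more than two. Weight and BMI are continuous. Primary reason of referral, medication and annual income print no levels. These rows are left out of the count.

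**2. Is a multi-group test named elsewhere?**

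- The general sentence under Descriptive statistics follows the sentence on checking for a Gaussian distribution. It leaves room for a suitable test but names none.
- Under Analysis methods, the regression models are assigned to objective 3 only.
- Objective 2 is descriptive and assigns no test.
- No section gives a rule for collapsing levels or a rule for pairwise tests.

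**3. How much the text leaves open**

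For the four multi-level characteristics, per SMFA index:

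- tests limited to two-level characteristics: 0
- one overall test each: 4
- all pairs, with k(k − 1)/2 pairs for k levels: 3 + 3 + 6 + 6 = 18

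For SMFA-D and SMFA-B together these are 0, 8 and 36. The SAP states none of the three.

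**4. Comorbidity bands**

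| Count | Bands that fit |
|---|---|
| 0 | 0 |
| 1 | 1-2 |
| 2 | 1-2 and 2-3 |
| 3 | 2-3 |
| 4 | none |
| 5 or more | >4 |

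If each participant is entered wherever the count fits, the rows sum to N + n₂ − n₄, where n₂ and n₄ are the numbers with exactly two and exactly four comorbidities. This equals N only if n₂ = n₄, and even then the rows would be wrong unless both were zero. The SAP gives no comorbidity distribution, so the number of participants affected cannot be stated.

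**The case against.** The strongest reply is that the sentence is underspecified rather than wrong. It does not say that all characteristics will be tested. Three fit the named tests exactly, and age, a continuous variable, is shown in just two bands. If the authors meant only those three, nothing is misapplied. That reading is possible, but the SAP does not state the limit. The phrase it uses covers the characteristics as presented, and most of those with printed levels have more than two.

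A second reply is that any competent analyst would choose Kruskal-Wallis and correct the comorbidity labels without being told. That is probably true, and it keeps the point minor, but the choice should still be fixed in advance. Table 1 is a shell, and a lost underline in the PDF could have turned ≥4 into >4. However, ≥ 80 survived in the same table, and a lost underline would not explain the overlap at 2.

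Two stronger readings are tempting, and the document supports neither:

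- A reader might infer that the investigators will run every pairwise test unadjusted and so inflate false positives. The SAP does not plan all pairs, and any error rate would also need group sizes and a correlation between the two indices that it does not give.
- A reader might infer that the sentence means comparing scores and characteristics between the three clinical groups, so that two-group tests fail on every reading. The SAP does not tie the sentence to those groups, and Table 1 also offers two-group splits. The ambiguity is real, but this conclusion is not established.

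**Conclusion.** Both points stand as wrong as written, and both are minor. The named tests fit three of the seven characteristics with printed levels and do not fit the other four. The comorbidity bands double-assign a count of 2 and leave out a count of 4.

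These conclusions rest only on the printed levels and on the absence of any other named test or collapsing rule. They need no distributional assumption. None of the six items in the SAP's Hypothesis section compares SMFA between levels of a baseline characteristic. The main correlations and the sample-size calculation are untouched. What is affected is a supporting comparison under objective 1 and one block of the descriptive table for objective 2.

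**What to change.** Before analysis, amend the objective 1 sentence as follows:

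- List the characteristics compared and say that SMFA-D and SMFA-B are compared between their levels, if that is what is meant.
- Keep the unpaired t-test or Mann-Whitney U for characteristics with two levels.
- For three or more levels, use one overall test: one-way ANOVA, or Kruskal-Wallis if the data are not normal. Adjust any pairwise follow-up for multiplicity.
- Report these comparisons as exploratory.

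In Table 1, replace the comorbidity rows with mutually exclusive and exhaustive bands chosen by the investigators.

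The cost is two or three sentences and one set of table labels. No new data are needed, provided the comorbidity count itself was recorded.
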